#### 2. Objectives (include all primary and secondary objectives)

- (1) **Using latent class analysis, investigate whether a hypodopaminergic state, produced by a temporary interruption of dopamine medications, is associated with a distinct anxiety syndrome in PD in a cross-sectional study of 200 subjects with idiopathic PD. Hypothesis: Certain anxiety syndromes and PD have a shared causal mechanism. Demonstrating that certain anxiety symptoms are associated with motor fluctuations, that is both anxiety and motor fluctuations are increased in hypodopaminergic states and cluster together based on a latent variable will support this hypothesis**

(2) **Conduct an 8-week intervention study of rotigotine (n=30) compared to placebo (n=30) for the treatment of anxiety disorders in PD that will provide estimates of effect size and the impact of co-occurring motor fluctuations on the treatment of anxiety. Hypothesis: Treatment with rotigotine for anxiety associated with motor fluctuations will result in a greater reduction of anxiety as compared to treatment with placebo**

3. **Background** (briefly describe pre-clinical and clinical data, current experience with procedures, drug or device, and any other relevant information to justify the research)

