#### 4. Study Procedures

- a. Study design, including the sequence and timing of study procedures (distinguish research procedures from those that are part of routine care).

For objective 1: Subjects will be assessed in both the “on” and “off” motor states following the clinical protocol from the Core Assessment Program for Surgical Interventional Therapies in PD (CAPSIT-PD).(23) We use the CAPSIT-PD protocol routinely in the PDRC and movement disorder clinics and will include consenting individuals as part of this study. However, a portion of the subjects recruited will have the CAPSIT-PD protocol exclusively for this study and not as a part of routine clinical care. "Wearing-off" and the "off-motor state" in PD are defined as a generally predictable recurrence of motor and non-motor symptoms as the effect of dopaminergic medications stops.(12) Subjects will temporarily stop all dopaminergic medications for a minimum of 12-hours in order to be assessed in the “off” motor state in the morning. (Most individuals with PD do not take medications overnight and usually take their last dose between 5-9pm. Therefore most participants will only be off medications for a few hours more than they normally would be as the study will be conducted in the morning) The on- and off-state assessments are listed below. Subjects will then take their usual morning dopaminergic medications and after one hour, to allow them to return to their best "on" state, repeat the CAPSIT-PD on-off battery. In addition to the on-off testing battery, several PD-related clinical features will be assessed, only in the on-state, using instruments recommended by the National Institute of Neurological Disorders and Stroke Common Data Element Project (NINDS-CDE)(24) for PD.

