##### CAPSIT-PD on- and off-state testing battery

Each assessment will be conducted twice, once in the off-state and once after resuming PD meds in the on-state

1. Anxiety: Hamilton Anxiety Rating Scale (HAM-A)(25)
2. Depression: 17-item Hamilton Depression Rating Scale (HAM-D)(26)
3. Motor and non-motor fluctuations: 19-symptom wearing-off questionnaire (WOQ-19)(27)
4. Physical Disability: Schwab and England Scale (SE)(28)
5. Motor symptom severity: MDS-UPDRS part III(30)
6. Symbol Digit Modalities Test(45)
7. Stroop Color and Word Test(46)

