## 7. Study Statistics

- a. Primary outcome variable. Hamilton Anxiety Rating Scale(HAM-A)
- b. Secondary outcome variables. 17-item Hamilton Depression Rating Scale (HAM-D), 19symptom wearing-off questionnaire (WOQ-19), Schwab and England Scale (SE), MDS-UPDRS part III
- c. Statistical plan including sample size (n=200) justification and interim data analysis.  
For objective 1: We will conduct a latent profile analysis (LPA) using the following observed variables (measured in the on-state) as latent profile indicators: age of PD onset, LEDD, HAMA, HAM-D, WOQ-19, SE, UPDRS part III, and MoCA score, to model unobserved (i.e. latent) profiles. LPA is a type of latent class analysis that uses continuous indicator variables. Using LPA we will determine 1) the number of classes/profiles that best fits symptom profiles of observed values, 2) the proportion of the sample that belongs in each class/profile (e.g. class prevalences), and 3) the means of each latent profile, conditioned upon membership in each class. We will then test whether specific subject characteristics (age, gender, variability of symptoms between on- and off-states (as change scores), and motor fluctuations), from the battery above predict differential membership in the identified latent profiles via latent profile regression. With latent profile regression, predictors of latent profile membership are modeled via multinomial logistic regression. Statistical power for latent profile regression was determined via monte carlo simulation,(42) assuming 3 classes/profiles with prevalences of 30%, 10%, and 60%. We would have 80% or greater power to detect a log odds ratio for an association between a standardized predictor and latent profile membership of 1.17 for profile 1 (prevalence of 30%) and 1.71 for profile 2 (prevalence of 10%), with profile 3 as the reference class. Antidepressant, anti-anxiety, and other psychiatric medication use will be controlled for in the analysis.

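### Objective 1's latent profiles use on-state scores only, so a class defined by off-state worsening cannot emerge, and no paired off-versus-on comparison is planned

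*Combined protocol and SAP*

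**What the plan says.** Section 2 asks whether "a hypodopaminergic state, produced by a temporary interruption of dopamine medications, is associated with a distinct anxiety syndrome in PD". It then names what would count as support: that "both anxiety and motor fluctuations are increased in hypodopaminergic states and cluster together based on a latent variable".

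Section 4.a has each subject tested in the morning after at least 12 hours without dopaminergic medication. The next step is: "Subjects will then take their usual morning dopaminergic medications and after one hour, to allow them to return to their best" on state, when the battery is repeated. For HAM-A, HAM-D, WOQ-19, SE, UPDRS part III and two cognitive tests, "Each assessment will be conducted twice, once in the off-state and once after resuming PD meds in the on-state". WOQ-19 is listed there as the measure of motor and non-motor fluctuations. Section 8.a adds that off-state testing stops if a subject is distressed, and that subjects who cannot tolerate 8 hours of washout are excluded. It calls this rare.

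Section 7.c forms the latent profiles from variables "measured in the on-state) as latent profile indicators: age of PD onset, LEDD, HAMA, HAM-D, WOQ-19, SE", UPDRS part III and MoCA. It will choose "the number of classes/profiles that best fits symptom profiles of observed values". A multinomial regression then asks whether age, gender and "variability of symptoms between on- and off-states (as change scores), and motor fluctuations), from the battery above predict differential membership" in the profiles found. Power is given for this second step only: 80% or more at log odds ratios of 1.17 (30% profile) and 1.71 (10% profile).

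**The concern.** The hypothesis concerns what happens when dopaminergic drive is low. The profiles are formed one hour after medication, at the subject's best. Section 3 describes the most common atypical anxiety in PD as episodic and possibly linked to wearing-off, so it may leave little mark on on-state scores. If so, there is no profile for the change scores to predict. A null regression could then be read as evidence against an off-state syndrome that the analysis had no means of finding. Separately, the hypothesis says that anxiety and fluctuations increase off medication, and no planned test compares the two states directly.

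**Working it through.** **1. Hypothesis against plan**

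| Part of the hypothesis | What section 7.c provides |
|---|---|
| Anxiety and motor signs increase off medication | Change scores are calculated, but no test of whether mean change differs from zero |
| On/off change is associated with a syndrome | Tested, as a predictor of on-state profile membership |
| Anxiety clusters with reported fluctuations | Partly: HAM-A and WOQ-19 are both on-state indicators |
| Off-state anxiety and motor worsening cluster | Nothing: neither off-state scores nor differences are indicators |

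**2. The plan's own power figure.** With class membership treated as known (a best case), n=200, prevalences 30/10/60%, an assumed two-sided 0.05 and 1,000 replicates, power is about 100% at 1.17 and 1.71. It reaches about 80% near 0.46 and 0.72. The stated 80% or more is not contradicted. It cannot be reproduced exactly, because section 7.c gives no class separation and no alpha for objective 1. It concerns prediction of on-state profiles, not recovery of an off-state class.

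**3. Planned on-state model.** Gaussian mixtures, one versus two classes, shared covariance, n=200, 200 runs (Monte Carlo standard error at most √(0.25/200) = 3.5 points). With eight indicators a second class adds 9 parameters, so BIC needs a gain of 9 × ln 200 = 47.7. The likelihood ratio (LR) test uses a simulated 5% cut-off. Shifts are assumptions. Entries are BIC % / LR % for a 30% class.

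| On-state trace | Diagonal, no within-class correlation | Covariances freed, correlation 0.2 |
|---|---|---|
| 2 SD on WOQ-19 only | 0 / 8.5 | 0 / 8.5 |
| plus 1 SD on HAM-A | 12 / 84.5 | 0.5 / 11 |
| plus 1 SD on HAM-D | 79 / 99.5 | 0.5 / 13.5 |
| plus 1 SD on UPDRS III | 97.5 / 100 | 0 / 4.5 |

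With no trace the result is 0 / 5 by construction. For a 10% class under the diagonal model, the second row falls to 1.5 / 31.5 and the last to 26 / 83.5. Section 7.c does not state the covariance structure.

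**4. A model on off-minus-on differences.** Four indicators (HAM-A, HAM-D, SE, UPDRS III), covariances freed, correlation 0.2 among scales, no on-state trace, HAM-A and UPDRS III shifted. BIC threshold 5 × ln 200 = 26.5; LR cut-off 18.8. In score-SD units the difference has SD √(2(1−r)): 1.00, 0.77 and 0.55 at on/off correlations r of 0.5, 0.7 and 0.85. HAM-A points use the SD of 8.55 from section 7.c (objective 2). Ranges span a 10% and a 30% class; entries are BIC % / LR %.

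| Shift | HAM-A points | r=0.5 | r=0.7 | r=0.85 |
|---|---|---|---|---|
| 1 SD | 8.6 | 0 / 4 | 0.5–1.5 / 8 | 14.5–16 / 37.5–49.5 |
| 1.5 SD | 12.8 | 1.5 / 10.5–13.5 | 24–32 / 57–71.5 | 100 / 100 |
| 2 SD | 17.1 | 29–39.5 / 61–74 | 97–100 / 99.5–100 | 100 / 100 |

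Repeat simulations of the 2 SD, r=0.5 case (30% class in the one whose class size is recorded) gave 41–45% by BIC and 79–84% by LR.

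**5. False classes in that model.** With no true group and normal data, BIC finds a second class in 0% of runs and LR in 5%. With gamma-shaped margins of assumed skewness 0.5, 0.75 and 1.0, the rates are 13 / 58, 63 / 95 and 93 / 100. Forcing a diagonal covariance when the scales correlate at 0.2 gives a false class in 89% by BIC, even with normal data.

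**6. Paired comparison.** Assume SD 8.55 in both states. The mean HAM-A difference detectable with 80% power at two-sided 0.05 is (1.96 + 0.84) × 8.55 × √(2(1−r)) / √200. At r=0.5 this is 2.80 × 8.55 / 14.14 = 1.7 points; at r=0.7 it is 1.3.

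**The case against.** The strongest reply is that section 7.c does analyse the off-state data. Change scores are tested predictors in the regression for which power is given, and that answers objective 1's question about association. WOQ-19 as an indicator lets reported fluctuations cluster with anxiety, and section 2 nowhere demands off-state indicators. All of this stands. It leaves the clustering of measured off-state worsening uncovered, because a regression cannot predict membership in a profile that was never formed. Nor is the association clean. Off-minus-on change shares the on-state score with the indicators. With equal variances its correlation with that score is −√((1−r)/2): −0.50 at r=0.5 and −0.32 at r=0.8, by construction.

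The second reply is that a model on differences is weak and easily misled. This also stands. Good detection needs large shifts or an on/off correlation above 0.5, which is the only within-subject HAM-A correlation in the documents and was assumed for objective 2 time-points. Modest skewness produces false classes, and the documents do not give the shape of the change scores. The on-state model, also a normal mixture, is exposed to skewness too.

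Third, off-state data will not be complete. Under section 8.a, losses fall on subjects who tolerate the off state badly, the group of most interest.

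**Conclusion.** The mismatch follows from the text and does not depend on the simulations. Section 2 ties support to off-state increases that cluster on a latent variable; section 7.c forms its latent variable from on-state scores alone and plans no paired comparison. An off-state syndrome with little on-state trace cannot appear as a profile, and a null result would say nothing about it. This should be fixed, but it does not undermine the rest of objective 1.

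Three stronger readings might be inferred and are not supported:

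- That off-state data go unused, or objective 1 untested. Change scores are tested predictors.
- That the planned model cannot find a fluctuation-related syndrome at all. It can when several on-state scales shift, though this depends on class size and an unstated covariance structure.
- That a second model would settle the question. Its detection and false-class rates do not allow that.

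The sizes rest on assumed shifts, on/off correlations and skewness, and on one-versus-two-class comparisons, whereas the plan's power assumes three profiles.

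**What to change.** In section 7.c:

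- Add a paired off-versus-on comparison of HAM-A and UPDRS part III. Off is always tested first, so the difference cannot be separated from order.
- Add a pre-specified, exploratory second latent profile analysis on the off-minus-on differences of HAM-A, HAM-D, SE and UPDRS part III. Free the within-class covariances, state one class-number criterion for both analyses, and do not use these differences as predictors in the new model.
- Check the shape of the change scores. Use a skew-tolerant mixture or a transformation, and include non-normality in the Monte Carlo false-class rates. Do not read an extra class as a syndrome on fit alone.
- Report how many subjects had off-state testing stopped, were excluded for washout intolerance, or had a washout under 12 hours, and how this limits the result.
- State that a null from either profile analysis does not exclude an off-state syndrome.

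If the second analysis is not added, narrow section 2 to association of on/off change with on-state profiles.

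The cost is plan wording, one paired test, one exploratory model and a Monte Carlo run, with no new visits or measurements. The downside is the limited detection at n=200, so the second analysis supplements the on-state one and does not replace it.

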##### NINDS-CDE Recommended Assessments for PD-Specific Clinical Features (only for on-state)

1. Demographics
2. PD Medical History
3. PD Family History
4. PD and Non-PD Medication Log
5. Motor: MDS-UPDRS parts I-IV
6. Psychiatric: Structured clinical interview for DSM-IV-TR (SCID) axis I disorders, research version, non-patient edition (29)
7. Cognitive: Montreal Cognitive Assessment (MoCA)(31)
8. Other non-motor: Non-motor Symptoms Questionnaire (NMS-Quest)(35) and the Scales for Outcomes in Parkinson's disease autonomic dysfunction scale (SCOPA-AUT)(32,33)
9. Quality of life: 8-item Parkinson's Disease Questionnaire (PDQ-8)(34)
10. Questionnaire for Impulsive-Compulsive Disorders in Parkinson's Disease(QUIP)(47)

11. Neo Five-Factor Inventory(48)

12. Rapid Assessment of Physical Activity(RAPA)(49)

For objective 2:

The intervention will be 8 weeks in duration and include a 4-week dosage titration period and a 4-week maintenance period. Transdermal patch. Dosing will begin at baseline on day zero with either 1) placebo or 2) rotigotine at 2mg/24h and will be increased following the recommended dose escalation schedule for PD such that subjects will increase to 4mg/24hrs in week 2, and 6mg/24hrs in week 3. This dose of rotigotine is within the range shown to be safe and efficacious for the treatment of motor symptoms. 17,36,37) The timing of assessments is shown in Table 1. All assessments except for the physical exam, and the Clinical Global Impression for Anxiety Severity and change scales (CGI-S and CGI-C)(38) are part of the CAPSIT-PD on- and off-state testing battery, the table indicates administration points. Safety and tolerability will be assessed by recording adverse events.

b. Study duration and number of study visits required of research participants.

Objective 1 is one 3-hour cross-sectional visit, duration and visits for objective 2 are in Table 1

Table 1. Assessment schedule for objective 2					
Visit Number	Screening	Baseline	Follow-up visits		
Time	- - -	0	WK2	WK4	WK8: FINAL
Diagnostic Interview or AIM 1 Battery	X				X
Physical Examination	X				X
MDS-UPDRS I-IV	X				X
MoCA	X				X
CGI-Severity	X	X			
CGI-Change			X	X	X
HAM-A	X	X	X	X	X
HAM-D	X	X	X	X	X
SCOPA-AUT, NMS	X	X	X	X	X

c. Blinding, including justification for blinding or not blinding the trial, if applicable.

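### Objective 1: on/off change scores and age are used to predict latent profiles that are themselves built from the on-state scores and age of onset, which can inflate false positives several-fold if the profiles are poorly separated

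*Combined protocol and SAP*

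**What the plan says.** Section 2 describes objective 1 as a latent class investigation "in a cross-sectional study of 200 subjects with idiopathic PD". It says that showing "both anxiety and motor fluctuations are increased in hypodopaminergic states and cluster together based on a latent variable will support this hypothesis".

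Section 7.c gives the analysis. The profile indicators, taken in the on-state, are "age of PD onset, LEDD, HAMA, HAM-D, WOQ-19, SE, UPDRS part III, and MoCA score". Membership is then regressed, by multinomial logistic regression, on age, gender, "variability of symptoms between on- and off-states (as change scores), and motor fluctuations".

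The on/off battery in Section 4.a lists seven measures taken in both states. Five of them (HAM-A, HAM-D, WOQ-19, SE, MDS-UPDRS III) are profile indicators; the two cognitive tests are not. Section 7.c does not say which scales supply the change scores, and it names no instrument for motor fluctuations. The battery labels WOQ-19 as its measure of motor and non-motor fluctuations. The on-state-only list separately includes "Motor: MDS-UPDRS parts I-IV".

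The power statement assumes three profiles at 30%, 10% and 60%, and gives detectable log odds ratios of 1.17 and 1.71 per SD of predictor. The plan states no class separation, no direct effects of predictors on indicators, no rule on shared variables, and no choice between one-step and stepwise estimation.

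**The concern.** Latent profile regression treats the indicators as independent of the predictors once the profile is known. A change score (off minus on) on an indicator scale contains that indicator with a minus sign, so the two are generally correlated within a profile. Age equals age of onset plus disease duration, so it is correlated with the onset indicator in the same way. If WOQ-19 were the motor-fluctuation measure, one variable would sit on both sides of the model.

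A model without direct effects can absorb this within-profile correlation only as an association between predictor and profile. A significant change-score effect could therefore come from the shared score alone, and a real effect of opposite sign could be masked. The change scores carry the off-state information that objective 1 is about, so its main inference is exposed.

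**Working it through.** **1. The plan's power figures.** They cannot be reproduced exactly, because class means, variances and the test are not given. As a benchmark, suppose profiles were observed. The expected sizes are 200 × 0.30 = 60, 200 × 0.10 = 20 and 200 × 0.60 = 120. With two-sided 5% (an assumption; alpha is stated only for objective 2) and 80% power, the detectable log odds ratios are:
- profile 1: 2.80 × √(1/60 + 1/120) = 0.44
- profile 2: 2.80 × √(1/20 + 1/120) = 0.68

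The stated values are larger by 1.17/0.44 ≈ 2.6 and 1.71/0.68 ≈ 2.5, which would fit imperfectly separated profiles. In simulation, one-step estimation reaches 80% power at 1.17/1.71 when profiles differ by about 0.8–1.05 within-class SD on each separating indicator, depending on the class pattern. At 1.5 SD it is at least 98%.

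**2. Within-profile covariance.** For a change score,

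cov(off − on, on) = SD_on × (r × SD_off − SD_on),

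where r is the on/off correlation within profile. It is negative if SD_off/SD_on < 1/r, zero at equality and positive above. With equal SDs, corr(change, on) = −√((1 − r)/2), which is −0.50, −0.39 and −0.27 for r = 0.5, 0.7 and 0.85. For age, with duration independent of onset and duration SD equal to k times onset SD, corr(age, onset) = 1/√(1 + k²), which is 0.89 at k = 0.5 and 0.71 at k = 1.

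**3. Null rejection rates.** Settings: n = 200, prevalences 30/10/60, eight normal indicators with within-class SD 1, EM fit, 2-df likelihood-ratio test at 5%, predictor distribution equal in all profiles, equal on/off SDs. The ranges pool separately coded simulations with 150–600 runs per setting. Monte Carlo SE is at most √(0.25/150) ≈ 4 points.

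| Separation | Predictor | One-step | Modal assignment, then logit |
|---|---|---|---|
| 0.9–1.0 SD | HAM-A change, r = 0.5 | 71–96% | 39–48% |
| | HAM-A change, r = 0.7 | 56–80% | 26–34% |
| | HAM-A change, r = 0.85 | 33–48% | 17–20% |
| | unrelated | 8–12% | 3–7% |
| 1.5 SD | HAM-A change, r = 0.5–0.85 | 10–27% | 8–17% |
| | unrelated | 3–7% | 3–6% |
| 2.0 SD | HAM-A change, r = 0.5–0.85 | 4–9% | 3–9% |
| | unrelated | 3–6% | 3–5% |

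Entropy was about 0.67, 0.84 and 0.95 at 1.0, 1.5 and 2.0 SD. When the true profiles were treated as known, rejection was 2–7% throughout, so the excess comes from uncertain membership combined with the overlap. A bias-adjusted three-step fit at 1.0 SD gave 27% (r = 0.7) and 16% (r = 0.85), against 6% for an unrelated predictor.

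**4. Effect of the SD ratio (1.0 SD separation; one-step, modal).**
- r = 0.7: 22–24% and 12–13% at SD_off/SD_on = 1.2; 12% and 6–8% at 1/0.7 = 1.43.
- r = 0.85: 12% and 7% at 1/0.85 = 1.18; 20% and 8% at 1.3, where the covariance has turned positive.

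**5. Age.** With onset equal across profiles, age rejects in 92–98% (one-step) and 42–56% (modal) at 1.0 SD. At 2.0 SD the figures are 8–11% and 7–9%.

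**6. Remedies (one-step, r = 0.7, 0.8–1.5 SD).** Uncorrected, 14–89%. With a direct effect, 6–17%; with the on-state score dropped, 6–17%; with an on/off mean as indicator, 5–16%. An unrelated predictor gives 5–14% over the same range. For age, a direct effect reduced rejection from 98% to 9% at 1.0 SD.

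**The case against.** The overlap cannot be disputed from the text, but its size can.

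- Separation, on/off correlation, SD ratio and class pattern appear nowhere in the documents. The separation of about 1 SD is inferred by matching the plan's log odds ratios. The plan claims power of 80% or more, and other settings could give the same values. This stands: the anchor is an illustration, not evidence of what the plan assumed.
- Section 7.c first determines the profiles and then tests predictors, which reads at least as naturally as stepwise estimation. The milder figures deserve equal weight. They are still about three to four times the unrelated predictor's rate at 1.0 SD: 17% against 6% at r = 0.85, and 26% against 6% at r = 0.7.
- A correlation of 0.5 may be low for two ratings within one 3-hour visit, and spread may well be greater off medication. At r = 0.85, an off-state SD only 18% larger removes the excess. This stands, but the plan gives nothing to show that the data will meet that condition.
- The age figures assume that onset does not differ between profiles. If it does, an age effect is partly redundancy and not a false positive. Age is also not the hypothesis of interest.
- Objective 1 is cross-sectional and sets no alpha or decision rule. However, Section 2 treats the clustering result as support for a shared mechanism, so a spurious association would be read as evidence.

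**Conclusion.** The concern holds. As written, objective 1 places the same measurements on both sides of the latent profile regression, and nothing in the plan handles it. Confidence is high for the overlap and lower for its size.

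With separation near 1 SD and equal on/off SDs, false positives for a change score rise several-fold under either one-step or stepwise estimation. At 1.5 SD the inflation is modest to moderate, and at 2 SD it is largely gone. It also disappears where SD_off/SD_on equals 1/r. At low separation, part of the one-step excess is a small-sample effect that an unrelated predictor shows too. The stated power does not cover predictors coupled to indicators. The randomized comparison in objective 2 is not affected. This should be corrected before objective 1 is analysed.

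**What to change.** State in Section 7.c that no measure enters both sides of the model unadjusted.

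1. **Change scores.** Name the scales. Preferably keep all eight indicators and add a direct effect of each change score on its own on-state indicator. Alternatively, test one change score at a time with that scale's on-state indicator removed; removing all five together would leave only age of onset, LEDD and MoCA. An on/off mean can serve as indicator only if the two SDs are similar, since its covariance with the difference is (SD_off² − SD_on²)/2. If change scores become indicators instead, remove the matching on-state scores or model the residual correlation.
2. **Motor fluctuations.** Name the measure. MDS-UPDRS part IV is already collected. WOQ-19 should not be both indicator and predictor.
3. **Age.** Use either age or age of onset, or model the direct effect.
4. **Estimation and power.** State one-step or stepwise estimation, and rerun the Monte Carlo with the class separation stated and null rejection rates reported beside power.

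The cost is plan wording and a simulation rerun, with no new data or visits. The price is a few extra parameters, or fewer indicators and somewhat less class separation.

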For objective 2: The primary outcome variable is the HAM-A. Power was calculated based on an enrollment of 60 subjects total, equally distributed between treatment and control groups, with a 10% dropout by the final time-point, and a standard deviation of 8.55 (which is a pooled estimate calculated from different anxiety subtypes in PD patients assessed using the HAMA).(43) The within subject/between time-point correlation was assumed to be 0.5 with a compound symmetric correlation structure, and the alpha level was set at .05. Power calculations were based on the formula of Jung and Ahn,(44) which calculates power for the difference in slope (i.e. the difference in response trajectory) between treatment and control groups for a longitudinal clinical intervention. Based on the assumptions specified, we would be able to detect an effect size of .69 from baseline to 8 weeks for the two groups with 80% power. This proposal is for a proof of concept study that will provide important initial estimates which may be used to 1) assess the potential efficacy of this novel anxiety intervention and thus provide necessary data for a "go-no-go" decision for a more definitive hypothesis-testing trial, and 2) provide estimates of effect size and variance needed to properly design such a trial.

Screening for objective 1: Screen failures are expected to be rare for objective 1 as there are only 3 criteria for exclusion: 1) UK Brain Bank criteria for PD, 2) English speaking, and 3) nondemented. In our longitudinal study of Parkinson's disease, which has autopsy confirmation at study end, the rate of accurate clinical diagnosis of PD is approximately 90%. The presence of dementia has a similar accuracy and will be further screened using the MoCA with a cut off of <23. The drop-out rate is also expected to be low as objective 1 takes place in one 3-hour visit. Screening for objective 2: Objective 2 will require 60 subjects who *can* be recruited from the n=200 from objective 1. Based on our preliminary data, 30% of subjects with a DSM anxiety disorder and comorbid depression and up to 53% with anxiety disorders only will not be

on any treatment for anxiety. In addition, we have included a protocol for enrolling individuals whose anxiety is not adequately controlled on their current therapy.(item 4 inclusion criteria)

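### The 80% power at 0.69 SD for objective 2 does not follow from the stated inputs on the scheduled HAM-A visits; two-sided, the slope formula gives about 0.73 SD, or about 75% power at 0.69

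*Combined protocol and SAP*

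**What the plan says.** Section 7.c, objective 2, bases power on 30 subjects in each of two arms, "with a 10% dropout by the final time-point, and a standard deviation of 8.55", a within-subject correlation of 0.5 with compound symmetry, "and the alpha level was set at .05", and the Jung and Ahn formula, which "calculates power for the difference in slope (i.e. the difference in response trajectory) between treatment and control groups". Its conclusion is: "we would be able to detect an effect size of .69 from baseline to 8 weeks for the two groups with 80% power".

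Section 7.c does not list the time points, say whether alpha is one- or two-sided, or say how the 10% loss is spread over visits. Section 4.a says "The timing of assessments is shown in Table 1". That table marks the HAM-A at screening, baseline and weeks 2, 4 and 8.

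**The concern.** A slope comparison depends on when the measurements are taken, so 0.69 cannot be checked from 7.c alone. With the visits that Table 1 schedules, the stated inputs lead to a larger detectable effect than the one claimed.

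The figure matters because it is the only planning effect given for objective 2, and 7.c says the results will feed a go/no-go decision on a larger trial. If power at 0.69 SD is 75%, the chance of missing a true effect of that size is about 1 in 4, not 1 in 5. With the inputs unstated, a reader cannot tell whether 0.69 is too favourable (four visits, two-sided) or too cautious (one-sided, or screening included).

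**Working it through.** **Inputs from the documents.** n = 30 per arm, correlation 0.5 (compound symmetric), 10% lost by the final visit, alpha 0.05, 80% power, SD 8.55 (all 7.c). HAM-A at weeks 0, 2, 4 and 8 (Table 1).

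**Assumptions for the main reading.** The effect is in SD units, alpha is two-sided, and the time points are the Table 1 visits from baseline to week 8.

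**Formula.** Let p_j be the proportion observed at time t_j, and p_jk the proportion observed at both t_j and t_k: the smaller of the two for monotone dropout, the product for independent missingness.

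- τ = Σ p_j t_j / Σ p_j, and d_j = t_j − τ
- S = Σ p_j d_j²
- V = Σ p_j d_j² + 0.5 × Σ_{j≠k} p_jk d_j d_k
- SE of the 8-week difference = 8 × √(2V / (n S²))
- Detectable effect = (1.9600 + 0.8416) × SE
- Power at 0.69 = Φ(0.69/SE − 1.9600)

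**Attempt to reproduce 0.69: no dropout.** τ = 3.5 and d = (−3.5, −1.5, 0.5, 4.5), so S = 35 and V = 17.5. SE = 8 × √(35 / (30 × 35²)) = 0.2469. Detectable effect = 2.8016 × 0.2469 = **0.692**. Power at 0.69 = Φ(2.795 − 1.960) = 79.8%. This matches the stated figure, but without the stated dropout.

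**With 10% lost at the last visit.** τ = 13.2/3.9 = 3.385 and d = (−3.385, −1.385, 0.615, 4.615), so S = 32.92 and V = 17.42. SE = 8 × √(2 × 17.42 / (30 × 32.92²)) = 0.2619. Detectable effect = 2.8016 × 0.2619 = **0.734**. Power at 0.69 = Φ(2.635 − 1.960) = 75.0%.

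**Other dropout patterns (two-sided; monotone / independent).**

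| Retention at weeks 0, 2, 4, 8 | Detectable effect (SD) | Power at 0.69 |
|---|---|---|
| 1, 1, 1, .9 | 0.734 / 0.734 | 75.0% / 75.0% |
| 1, .967, .933, .9 | 0.735 / 0.736 | 74.9% / 74.8% |
| 1, .975, .95, .9 | 0.734 / 0.735 | 74.9% / 74.9% |
| 1, .9, .9, .9 | 0.730 / 0.738 | 75.5% / 74.5% |
| 27 completers per arm | 0.729 | 75.5% |

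The pattern moves the answer by less than 0.01 SD.

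**Other readings, with 10% dropout.**

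| Reading | Detectable effect (SD) | Power at 0.69 |
|---|---|---|
| Weeks 0, 2, 4, 8, one-sided 0.05 | 0.648–0.655 | 83.5–84.2% |
| Screening added as a second time-zero value, two-sided | 0.650–0.657 | about 84% |
| Five equally spaced times, gradual dropout, two-sided | 0.679–0.688 | 80–81% |
| Baseline and week 8 only, one-sided | 0.677 | 81.3% |
| Baseline and week 8 only, two-sided | 0.762 | 71.7% |

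**Size of the gap.** 0.69 × 8.55 = 5.9 HAM-A points, and 0.734 × 8.55 = 6.3 points, a difference of about 0.4. On the main reading, 33 per arm gives 0.696–0.704 and 34 per arm gives 0.685–0.694, so 80% power at 0.69 needs about 34 per arm (68 in total).

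**Sensitivity.** With monotone dropout, a correlation of 0.57 in place of 0.5 gives 0.69 or slightly less. So would an SD of about 8.0 for the same effect in points (8.55 × 0.69/0.735 = 8.03).

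**The case against.** The strongest reply is that this is incomplete reporting, not proven bad arithmetic. Section 7.c never says the Table 1 visits were used, and other designs come close to 0.69 with dropout included. Table 1 has five HAM-A columns, and treating five assessments as equally spaced gives 0.687 SD with dropout linear over time, which rounds to the stated value. Baseline and week 8 only, tested one-sided, gives 0.677 SD and 81% power. Across all the readings the answer falls on both sides of 0.69. The study is also described as proof of concept, no decision threshold is tied to 0.69, and the gap is smaller than the uncertainty in the correlation or the SD.

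Much of this stands. The documents do not show how 0.69 was obtained. The match with the no-dropout result is consistent with dropout not having been applied, but does not prove it. The gap is small.

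The alternative routes do not rescue the figure, however. Equal spacing over eight weeks needs a week-6 visit, and Table 1 has none; its visits are unequally spaced. The two-visit route discards scheduled HAM-A assessments and relies on a one-sided test that is stated nowhere. On the scheduled visits with the stated dropout, neither sidedness gives 0.69 at 80% power. Having to guess a design to recover the number is itself a reason to state the inputs.

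**Conclusion.** The concern holds. With the inputs of 7.c and the HAM-A visits at weeks 0, 2, 4 and 8, a two-sided 0.05 test with 10% dropout detects 0.73 to 0.74 SD with 80% power, and power at 0.69 SD is about 75%. This rests on three assumptions: the effect size is in SD units, alpha is two-sided, and screening is not a time point in the slope. Changing either of the last two gives about 0.65 SD, which also differs from 0.69. The result hardly depends on the dropout pattern. The shortfall is modest, about 5 percentage points of power, and does not by itself call for a larger trial. The stated figure should still be corrected or explained.

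**What to change.** In 7.c, state the HAM-A time points, the sidedness of alpha and the dropout pattern behind the calculation. If baseline and weeks 2, 4 and 8 with a two-sided 0.05 are intended, replace the conclusion with wording such as: *30 per arm with 10% dropout detects about 0.73 SD (6.3 HAM-A points) with 80% power; power at 0.69 SD is about 75%.* If another design was used, name it and reconcile it with Table 1.

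The cost is one or two sentences. Patients, visits and sample size stay as they are; on the main reading the stated figure becomes slightly less favourable.
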